| 
Study Objectives:
 
 
• Primary:
 
• Secondary:
 
 | 
Primary: To prevent the formation of donor-specific alloantibody in patients with chronic allograft injury (grade II or III IF/TA), thereby facilitating re-transplantation by avoiding sensitization
 
Secondary: To determine if treatment with belatacept better preserves GFR in those patients with marginal renal function as compared to those patients who continue calcineurin inhibitor therapy or mTOR inhibitor therapy and as a result delays time to initiation of dialysis.
  |

|   |   |
|---|---|
| Study Design:  | Open-label, prospective, randomized, controlled trial   |
| Accrual Goal:
(Total number of subjects)              | 72 patients, randomized 1:1 to either treatment arm- Belatacept or control arm- (remaining on CNI or mTOR inhibitor as detailed above).

This study will be performed in two phases: Phase I a total of 36 patients will be enrolled (18 in each arm). Phase II will be contingent on preliminary safety review and study progress from phase I and funding availability and will enroll an equal number of patients (36)   |
| Accrual Rate:
(Number of subjects expected per month) | 36 patients enrolled over 24 months (Phase I)

36 patients enrolled over 24 months (Phase II)   |
| FPFV:
LPFV:
Follow Up:
(dd-mm-yy) | Phase I

Start: August 1, 2013

FPFV: November 1, 2013

LPLV: November 1, 2018

Enrollment period: November 1, 2013 – November 1, 2015

Follow-up: 36 months

Phase II: timing TBD  |
| Correlative Studies:
(PK/PD, etc.)                    | Scheduled sample collection for measurement of allo-antibody using HLA-specific microparticles; serum chemistry including calculated GFR (creatinine measurement); complete blood count, viral titer monitoring   |

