## **4 INVESTIGATIONAL PLAN**

### **4.1 Study Design and Duration**

This is an open-label, prospective, randomized, controlled clinical trial. First-time renal transplant recipients who now have impaired renal function (estimated GFR  $\leq 35$  with a decline in renal function of  $\geq 10\%$  in the year prior to enrollment with biopsy proven grade II or III IF/TA) OR a GFR of  $\leq 20$  over the 6 month period prior to enrollment absent other causes for graft dysfunction and deemed to have a failing allograft by the patient's transplant nephrologist will be identified for randomization to either treatment (belatacept-based) or to continue standard of care (CNI-based or mTOR-based) regimen. There will be a total of 72 subjects, randomized in equal numbers, 36 patients in each arm. Patients must be candidates for re-transplantation. Those subjects who are EBV seronegative or have a history of PTLD will be excluded. Follow up will be planned for 36 months after randomization. The study will proceed in two sequential phases with distinct funding periods. Phase I will enroll 18 patients in each arm, 36 total patients. After discussions with BMS we will proceed with phase II, contingent on funding

availability and preliminary results from phase I. Phase II will enroll an additional 36 patients for a total of 72 patients, 36 in each arm.

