# **8 STATISTICAL CONSIDERATIONS**

## **8.1 Sample Size Determination**

This is a single-center, randomized, controlled trial to evaluate the efficacy of belatacept to prevent the formation of donor-specific antibody in patients with a failing renal allograft thereby preventing sensitization and facilitating re-transplantation. Based on clinical and statistical judgment, it is anticipated that a sample size of 36 patients per group will provide valuable preliminary data to assess the impact of belatacept on this growing population of patients.

The sample size for each arm will be 36 patients (Phase I 18 patients in each arm, Phase II 18 patients in each arm, total for each phase 36 patients). From previous work it is assumed that the control arm will have about 60% of patients developing antibodies within a 3 year period. (unpublished results, analysis of patients at Emory Hospital) It is proposed that the group treated with belatacept will have a dramatic decrease in allo-antibody production. Assuming a rate of 20% in the treatment group, the power would be calculated at 90%.

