### 8.3.3 Efficacy Analyses

There will be two main methods of analyzing the primary outcome at the study end. One will be a chi-squared test comparing the proportion of patients who developed donor specific antibodies in each study group. The second analysis will be a log-rank test comparing the Kaplan-Meier time to event curves between the two study groups. In both cases we will use a two-sided test with a significance level of 0.05.

The sample size for each arm will be 36 patients. This sample size calculation is based on several assumptions. We assume that the incidence of developing donor-specific antibody among the control group is 60% and among the belatacept-treated group it is 20% or less. We also assume an alpha level of 0.05 and corresponding  $Z\text{-alpha} = 1.96$  and a one-to-one ration of exposed to unexposed subjects. Calculations with these estimates yield a power of 90% to detect a three-fold difference in risk of developing donor specific antibodies between the control and belatacept-treated group.

In addition to the aforementioned assumptions, additional assumptions required for the log-rank test include no loss to follow-up in 36 months and that the distribution of the incidence of the primary endpoint follows an exponential distribution. Assuming an incidence of development of anti-donor antibody in the control group is 60% at 36 months then the hazard rate can be calculated as 0.02545. In the treatment arm, if the incidence of the primary endpoint is 30% then the hazard ratio becomes 0.0099 and if the incidence is 20% then the hazard rate is 0.00619.

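### The primary chi-squared and log-rank tests are not stratified by study phase; this causes no bias, but forgoes a little power if antibody rates differ between the two phases

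*Combined protocol and SAP*

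**What the plan says.** Section 4.1 describes the structure: "The study will proceed in two sequential phases with distinct funding periods". Section 8.1 gives the size of each: "Phase I 18 patients in each arm, Phase II 18 patients in each arm". Phase II depends on funding and on Phase I results, and the synopsis gives its schedule only as "Phase II: timing TBD".

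Section 8.3.3 names two analyses of the primary outcome at study end. The first: "One will be a chi-squared test comparing the proportion of patients who developed donor specific antibodies in each study group". The second: "The second analysis will be a log-rank test comparing the Kaplan-Meier time to event curves between the two study groups". On the level it says: "In both cases we will use a two-sided test with a significance level of 0.05". The sample size assumes that "the incidence of developing donor-specific antibody among the control group is 60% and among the belatacept-treated group it is 20% or less", and the section concludes: "Calculations with these estimates yield a power of 90% to detect a three-fold difference in risk". It also works out a hazard for a belatacept incidence of 30%.

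Neither Section 8.3.3, nor the synopsis Statistics row, nor the randomization text in Section 5.3 names phase as a stratification factor. Pooling of the phases is not stated in words. It follows from the use of 36 per arm.

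**The concern.** If each phase delivers its planned 18 per arm, allocation is balanced within phase. Enrolment for Phase I alone runs for 24 months and Phase II begins at an unknown later date, so patient mix or practice could change and move the DSA rate in both arms. An unstratified test counts that movement as noise within each arm. Its variance estimate is then too large for the comparison actually made, and it rejects less often than its nominal level allows. A test stratified by phase removes that component.

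What is at stake is efficiency: some power forgone relative to an equally simple and valid test. This matters more if the belatacept rate is nearer 30% than 20%, because power is then already below 75%.

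**Working it through.** **Inputs.** 36 per arm, 18 per arm per phase (Sections 4.1 and 8.1); two-sided 0.05, control 60%, belatacept 20%, alternative 30%, no loss to follow-up, exponential times (Section 8.3.3). The synopsis Statistics row says 30 per arm; I use the 36 of Section 8. The shift between phases is my assumption: ±s means that both arms lie s points above their average in one phase and s points below in the other.

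**The plan's own figures.** Power = Φ[(d − 1.96·√(2p̄(1−p̄)/n)) / √((p₁q₁+p₂q₂)/n)], with d = 0.40, p̄ = 0.40, n = 36.
- Without continuity correction: (0.400 − 0.2263)/0.1054 = 1.648, so 95.0%.
- With correction, d reduced by 1/36 = 0.0278: 0.1459/0.1054 = 1.384, so 91.7%.

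The stated 90% is therefore reproduced, slightly conservatively, with the correction. The hazards also reproduce: −ln(0.4)/36 = 0.02545, −ln(0.7)/36 = 0.0099, −ln(0.8)/36 = 0.0062.

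**Why the unstratified test is conservative.** Take no treatment effect and rates of 60% then 20% in both arms. The pooled variance is 0.40 × 0.60 = 0.24. The true within-phase average is (0.24 + 0.16)/2 = 0.20. The effective critical value is 1.96 × √(0.24/0.20) = 2.147, which gives a two-sided level of about 3.2%. Exact enumeration gives 3.1% for the pooled chi-squared and 5.0% for CMH. At 50% then 30% the figures are 4.5% and 4.8%.

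**Exact power for the chi-squared comparison.** I enumerated all outcomes of four Binomial(18) cells. With c_k control events and m_k total events in phase k, the CMH statistic without continuity correction is [Σ(c_k − m_k/2)]² / Σ[18·18·m_k(36 − m_k)/(36²·35)]. It is compared with the ordinary Pearson statistic on 36 v 36.

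| Average rates | Shift | Control by phase | Belatacept by phase | Pooled | CMH by phase | Gain (points) |
|---|---|---|---|---|---|---|
| 60% v 20% | none | 60/60 | 20/20 | 94.9% | 94.6% | −0.3 |
| | ±10 | 70/50 | 30/10 | 95.3% | 95.9% | 0.5 |
| | ±15 | 75/45 | 35/5 | 95.9% | 97.1% | 1.2 |
| | ±20 | 80/40 | 40/0 | 96.8% | 98.5% | 1.7 |
| 60% v 30% | none | 60/60 | 30/30 | 72.7% | 72.4% | −0.3 |
| | ±10 | 70/50 | 40/20 | 73.1% | 74.8% | 1.7 |
| | ±15 | 75/45 | 45/15 | 73.6% | 78.2% | 4.6 |
| | ±20 | 80/40 | 50/10 | 74.4% | 82.2% | 7.8 |

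Gains are taken from unrounded values.

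**Log-rank, unstratified v stratified** (10,000 simulated trials per case; simulation error about 0.4 points near 75% and 0.2 near 95%):
- 60% v 20%: no shift 95.4% v 95.3%; ±10 95.8% v 95.9%; control 80/40 with belatacept 30/10, 96.4% v 97.5%.
- 60% v 30%: no shift 74.4% v 74.3%; ±10 76.3% v 77.0%; control 80/40 with belatacept 45/15, 77.9% v 82.8%.

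**A shift that changes the effect.** If the Phase II control rate falls to 40% while belatacept stays at 20%, chi-squared power is 78.9% pooled and 78.2% stratified; for the log-rank test it is 78.9% and 79.9%.

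**The case against.** The strongest reply is that the prespecified tests are valid and that the gain is trivial where the trial is powered. That largely stands. At 60% v 20% the gain stays below 2 points even when the control rate moves from 80% to 40%, and unstratified power remains above the stated 90%. Gains of 5 to 8 points need both the weaker 60% v 30% effect and a difference of 30 to 40 points between phases. The documents give no reason to expect so large a shift: one centre (Section 8.1), one set of eligibility criteria, and one named HLA laboratory and assay (Section 6.2). The 30% rate appears only in the hazard illustration, not in the power claim.

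A reader might infer more than the documents support:
- *That pooling biases the comparison.* It does not while arms are balanced within phase. Section 5.3 describes no blocking, so a Phase II cut short could be unbalanced, but the effect is modest. With an assumed 10 v 6 in Phase II, the shares in that phase are 10/28 = 36% and 6/24 = 25%, so a 20-point phase difference moves the crude contrast by about 2 points.
- *That a shift erodes the planned power.* With average rates held, unstratified power rises slightly (94.9% to 96.8%; 72.7% to 74.4%). The shortfall is only relative to a stratified test.
- *That stratifying rescues a smaller Phase II effect.* The last calculation shows that it does not: that loss comes from the effect itself.
- *That randomization is stratified by phase.* The figures of 18 per arm are enrolment numbers; no such randomization is described.

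What survives is that stratification costs almost nothing and uses a grouping already in the design.

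**Conclusion.** The point holds as an optional, low-cost improvement. Ignoring phase leaves the primary tests valid and at worst conservative, with a true level of about 3.1% against 5.0% in the 60%-then-20% null case. Relative to a phase-stratified chi-squared test, the power forgone is 0.5 to 1.7 points at the planned 60% v 20% and 1.7 to 7.8 points at 60% v 30%, for assumed shifts of ±10 to ±20 points. The log-rank gain is under 1 point at ±10 for both effects. If the phases do not differ, stratifying costs about 0.3 points for the chi-squared test and essentially nothing for the log-rank.

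These figures rest on exactly 18 per arm per phase, complete 36-month follow-up, exponential times for the log-rank results, and shifts that are not in the documents. The sample size is not undermined.

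**What to change.** In Section 8.3.3 and the synopsis Statistics row, name the primary tests as a CMH test **without continuity correction** and a log-rank test, both stratified by study phase, and keep the unstratified tests as sensitivity analyses. State that if Phase II is not run, the unstratified tests are used. CMH with a single stratum is not identical to Pearson's test: its statistic is (N−1)/N times Pearson's, or 35/36 with Phase I alone.

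The continuity correction must be settled in the wording. At 60% v 30%, a corrected CMH test has power of 63.7%, 66.4% and 70.0% for no shift, ±10 and ±15, below the plain Pearson test's 72.7%, 73.1% and 73.6%, so silence could turn the change into a loss.

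The cost is one sentence in each place and about 0.3 points of power if the phases do not differ. Phase is known for every subject, so no new data are needed. Make the change before outcomes are compared by arm: the trial is open-label, and stratification added later would look data-driven.

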#### **2) Target Population**

- a) The subject is a kidney transplant recipient (non-HLA identical donor) who now has impaired renal allograft function with at least one of the following:
  - i) Estimated GFR  $\leq 35$  with a decline in GFR of  $\geq 10\%$  in the 12 months prior to enrollment and must have biopsy proven grade II or III interstitial fibrosis/tubular atrophy (IF/TA)
  - ii) Estimated GFR persistently  $\leq 20$  ml/min over the 6 month period prior to enrollment absent other causes for graft dysfunction, and deemed to have a failing allograft by the patient's transplant nephrologist
- b)  $\geq 1$  year post-transplant
- c) The subject must be a re-transplant candidate
- d) The subject must be on an immunosuppression regimen meeting one of the following criteria:
  - i) A CNI (tacrolimus or cyclosporine) or mTOR inhibitor (sirolimus or everolimus) and at least one of the following:
    - (1) MMF at a dose of at least 1 gm/day or comparable dose of MPA or azathioprine
    - (2) Prednisone at a dose of at least 5 mg/day
  - ii) A CNI (tacrolimus or cyclosporine) or mTOR inhibitor (sirolimus or everolimus) alone for 3 months or more, with no clinically significant changes in PRA during that time, as determined by the Emory HLA lab.

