months, and 3 months. Subsequent belatacept doses will be 5mg/kg IV every month through the duration of the trial or until re-transplantation occurs, whichever is first. A month will be defined as one true calendar month. There will be a  $\pm 2$  days window for the 2nd (2 week) belatacept infusion, and a  $\pm 5$  days window for subsequent infusions. If on MMF subjects will continue their MMF (equivalent of at least 1g daily) or if on MPA or azathioprine, a comparable dose. If on steroids they will continue on corticosteroids. If on MMF/MPA/azathioprine and steroids they will continue on both. Upon initiation of dialysis or in subjects already requiring dialysis at the time of enrollment, the MMF or azathioprine dose will be decreased by 50% and then discontinued 2 weeks later. Steroid dose will be weaned by 50% at one month after returning to dialysis, with a subsequent 50% reduction at 2 months and discontinuation at 3 months. Belatacept will be continued at 5mg/kg IV monthly ( $\pm 5$  days) for the duration of the study or retransplantation whichever occurs first. If a subject progresses to dialysis dependence while still receiving belatacept at the 10 mg/kg dosing, the subject will continue to receive 10 mg/kg dose as scheduled through month 3 (5 total doses) and then decrease to 5 mg/kg IV q month for the duration of study participation.

Infusion doses will be based on the subject's actual body weight at enrollment, and will not be modified during the course of the study, unless there is a change of body weight greater than  $\pm 10\%$ . Study drug should be administered to the subject at a relatively constant rate over approximately 30 minutes. Once subjects have initiated hemodialysis, study infusion visits will be scheduled on non-dialysis days. If patients perform peritoneal dialysis, study infusion visits will be scheduled without regard to dialysis schedule.

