## **8.2 Endpoint Definitions**

**Primary Endpoint:** The rate of donor-specific antibody formation 36 months following randomization.

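### The chi-squared primary analysis has no rule for subjects whose month-36 DSA status is unknown; scoring them as DSA-free by default lowers power and biases the comparison if exit differs by arm

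*Combined protocol and SAP*

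**What the plan says.** The primary endpoint (Section 8.2) is "The rate of donor-specific antibody formation 36 months following randomization". Section 8.3.3 gives two main analyses. On the first: "One will be a chi-squared test comparing the proportion of patients who developed donor specific antibodies in each study group". On the second: "The second analysis will be a log-rank test comparing the Kaplan-Meier time to event curves between the two study groups". On the level: "In both cases we will use a two-sided test with a significance level of 0.05". The planning rates are that "the incidence of developing donor-specific antibody among the control group is 60% and among the belatacept-treated group it is 20% or less", with 36 per arm and 90% power. The text then turns to time-to-event planning and says that "additional assumptions required for the log-rank test include no loss to follow-up in 36 months".

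Other sections determine whose month-36 status will be known:

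- Section 4.2.1, on eligibility: "The subject must be a re-transplant candidate". Re-transplantation during follow-up is therefore expected in some subjects.
- Section 5.4 gives belatacept "through the duration of the trial or until re-transplantation occurs, whichever is first". This concerns dosing. No section says whether sampling for antibody to the original donor continues after re-transplantation.
- Section 6.1 brings the next set of assessments forward at withdrawal. After that, Section 7.7 lists contact about survival, dialysis and serious adverse events, and does not list DSA.
- Section 6.5 (EBV Titers) removes from the study belatacept subjects on dialysis whose positive titers persist. The control arm has no counterpart.
- Section 6.3 calls for intent-to-treat analysis.

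No section states a denominator or a missing-status rule for the chi-squared test, or a censoring rule for the log-rank test.

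**The concern.** A proportion at a fixed time needs everyone's status at that time. A subject who dies or withdraws at month 10 without DSA contributes 10 months of information, not 36. With all randomized subjects in the denominator and only observed DSA in the numerator, that subject counts as a success. If exit is equal in the two arms, both rates shrink and power is lost. If exit is unequal, the arm with more exit looks better on DSA even when the treatment does nothing.

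Unequal exit is foreseeable, because one withdrawal rule applies to the belatacept arm only and because the research hypothesis concerns the timing of re-transplantation. The trial is open-label, so a convention chosen late could be chosen with the data in view.

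**Working it through.** **Inputs.** From Section 8.3.3: 36 per arm, 60% versus 20% DSA at 36 months, two-sided 0.05, exponential event times. Assumed, because the documents give no figure: the probability c of leaving by month 36, with exponential leaving times independent of DSA.

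**Step 1: the plan's own figures.** The control hazard is −ln(0.4)/36 = 0.02545 per month, as stated. For power, the null standard error is √(2 × 0.4 × 0.6/36) = 0.1155 and the alternative standard error is √((0.24 + 0.16)/36) = 0.1054.

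- Uncorrected: (0.4 − 1.96 × 0.1155)/0.1054 = 1.65, power 95.0%.
- Continuity-corrected: subtract 1/36 from the difference, giving 1.38, power 91.7% (exact enumeration 91.3%).

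At 36 per arm the stated 90% is therefore close to the corrected test. The uncorrected formula gives 90.6% at the 30 per arm quoted in the Synopsis, so the source of the 90% is not certain. Both versions are carried below. All of these figures assume that status is known for everyone at month 36.

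**Step 2: observed proportion when exits count as DSA-free.** With λ = −ln(1−p)/36 and μ = −ln(1−c)/36,

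P(DSA seen) = λ/(λ+μ) × [1 − (1−p)(1−c)].

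- p = 0.6, c = 0.20: 0.02545/(0.02545 + 0.00620) × 0.68 = 54.7%
- p = 0.6, c = 0.40: 0.02545/(0.02545 + 0.01419) × 0.76 = 48.8%
- p = 0.6, c = 0.50: 0.02545/(0.02545 + 0.01925) × 0.80 = 45.5%
- p = 0.2, c = 0.20: 0.5 × 0.36 = 18.0%

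The same formula gives 56.1% for c = 0.15 and 51.8% for c = 0.30, both at p = 0.6.

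**Step 3: type I error, true rate 60% in both arms, 36 per arm (exact enumeration).**

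| Exit by month 36, arm A vs arm B | Observed DSA, A vs B | Uncorrected | Corrected |
|---|---|---|---|
| none | 60% vs 60% | about 5% | 2.6% |
| 30% vs 15% | 51.8% vs 56.1% | 6.0% | 3.4% |
| 40% vs 20% | 48.8% vs 54.7% | 7.3% | 4.3% |
| 50% vs 20% | 45.5% vs 54.7% | 11.2% | 7.2% |

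The calculation is symmetric: either treatment can be arm A. The log-rank test with exits censored stayed at about 5% in simulation, given non-informative censoring.

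**Step 4: power at 60% versus 20%, 20% exit in both arms.** Observed rates are 54.7% and 18.0%. Power falls from 95% to 92% uncorrected, and from 91% to 87% corrected. In simulation the log-rank test falls from 95.3% to 93.1%.

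**Step 5: the other obvious convention.** Suppose subjects who leave without DSA are excluded. Under no effect with 50% versus 20% exit, the rates become 0.455/(0.455 + 0.4 × 0.5) = 69.5% and 0.547/(0.547 + 0.4 × 0.8) = 63.1%. The bias reverses, and uncorrected type I error is 7.9% by simulation. The two conventions push the result in opposite directions.

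**The case against.** Several objections stand.

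- The plan does not state that exits are scored DSA-free. That is the likely default under intent to treat, not a written rule. The defect is an omission.
- A reader might infer that follow-up is cut short by design at re-transplantation. The documents do not support this. Section 5.4 ends dosing there, Section 4.1 plans 36 months of follow-up, and re-transplantation is not among the withdrawal reasons in Section 4.2.3. Antibody to the original donor could still be measured. The position is unspecified.
- A reader might infer that the bias must favour belatacept, because the drug is hoped to ease re-transplantation. Section 1.1 makes that a consequence of less sensitization, so the route disappears if there is no DSA effect. The same section also expects a longer time to dialysis or re-transplantation, which points the other way. The direction is open.
- A reader might infer that the no-loss assumption is attached to the wrong test. It sits in the sample-size text, and no loss is a legitimate simplification for log-rank power, which depends on the number of events. What remains is that the chi-squared calculation needs it too and does not say so.
- With continuity correction, two of the three unequal-exit scenarios stay below 5%.

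The log-rank test is already one of the two main analyses and the only interim test. It is not assumption-free either, since censoring at death, withdrawal or re-transplantation may be informative. None of this supplies the missing rule for the chi-squared test.

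**Conclusion.** The point holds as an omission with conditional consequences. One of the two main primary analyses cannot be carried out as written without a choice the plan does not make, and the two obvious choices bias the result in opposite directions when exit differs by arm. With equal exit the loss is modest: 3 to 4 percentage points of power at 20% exit. Unequal exit is the main risk. Type I error reaches 6.0% to 11.2% uncorrected, or 3.4% to 7.2% corrected, over the scenarios shown. These figures rest on assumed exit rates, independent exponential exit, and exits scored DSA-free. The plan does not say which version of the chi-squared test will be run.

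**What to change.** In Section 8.3.3:

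1. Make the planned log-rank test the single decision test. Define the event as DSA against the original donor, censor at the last DSA sample, state how death and re-transplantation are handled, and state that censoring is assumed non-informative.
2. Replace the raw chi-squared comparison with a comparison of Kaplan-Meier month-36 DSA incidence. Add an Aalen-Johansen estimate with death and re-transplantation as competing events as a sensitivity analysis.
3. State that the no-loss assumption underlies both power calculations, and give power under a plausible range of exit.
4. State whether DSA sampling against the original donor continues after re-transplantation.

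Items 1 to 3 change wording only and use dates the trial should already hold. They cost slightly more analysis work and a slightly lower stated power once losses are allowed for. Item 4 needs extra samples only if the answer is to continue sampling that would otherwise have stopped.
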